5.8 Exclusion criteria

- Patients with other known causes of proteinuria, e.g. UTI, fever
- At screening visit SBP higher than 160 mmHg or DBP higher than 100 mmHg or SBP lower than 90 mmHg
- Glycated hemoglobin (HbA1C) >11%
- Known hypersensitivity to dapagliflozin or finerenone
- Known case of Addison's disease
- Known case of hepatic insufficiency
- Treatment with SGLT2i (empagliflozin:62 hours, dapagliflozin:65hours) or MRAs (finerenone:10-20 hours, spironolactone:7 hours , eplerenone:15-30 hours) within their wash out periods.
- Patients on non-dihydropyridine Calcium Channel blockers or Glucagon-like peptide-1 (GLP-1) agonists
- Pregnant lady or lactating mother

5.9. Sample size: Sample size calculation for hypothesis testing of difference between two proportions:

$$n = \frac{p(100 - p) + q(100 - q)}{(p - q)^2} (z_{\alpha} + z_{\beta})^2$$

Where,

Z_{α} = Z value of standard normal distribution at a definite level of significance

Z_{β} = Z value of standard normal distribution at a definite level of power

p = Percent change from baseline in UACR after treatment in the experimental group

q = Percent change from baseline in UACR after treatment in the control group

Here,

Z_{α} = 1.96 at 95% Confidence Interval

Z_{β} = 1.28 at 90% power

p = 36% (Mårup et al., 2024)

q = 8% (Mårup et al., 2024)

So,

$$n = \frac{36(100-36) + 8(100-8)}{(36-8)^2} (1.96 + 1.28)^2 \approx 40$$

Considering 10% lost to follow-up final sample will be $(40 + 40 \times 10\%) = 44$. That means 44 patients in each group will be needed to test the hypothesis.

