Materials and Methods: This open-label randomized controlled trial will be conducted in the Department of Nephrology of Chittagong Medical College Hospital, Chattogram, Bangladesh including 88 patients with chronic kidney disease and type 2 diabetes. Participants will be randomized into one of two study groups. The experimental group will be treated with dapagliflozin 10 mg plus finerenone 10 mg once daily for eight weeks. The control group will receive dapagliflozin 10 mg once daily for the same duration. The primary outcome measure will be the change in UACR, while the other variables will include serum creatinine, eGFR, serum potassium. Adverse events and safety measures will also be recorded. The primary analysis will follow either an intention-to-treat or a perprotocol approach and will be performed using SPSS version 27.

Conclusion: This study will elucidate the efficacy and safety of dapagliflozin - finerenone combination in a Bangladeshi cohort, potentially guiding strategies to mitigate albuminuria in T2DM.

PART-D

1. Introduction:

Chronic kidney disease is a common and serious complication in individuals with type 2 diabetes, contributing significantly to morbidity and mortality. It progresses silently and is frequently associated with increased cardiovascular risks and reduced renal function (Navaneethan et al., 2025; Hansrivijit et al., 2025).

The global prevalence of chronic kidney disease (CKD) among patients with type 2 diabetes mellitus (T2DM) is a growing concern, with approximately 27% of diabetic individuals affected worldwide according to a recent meta-analysis (Fenta et al., 2023). Regional studies further highlight this burden; in the United States, CKD prevalence among T2DM patients rose to 1.28% by 2018 (Feng et al., 2021). In Ethiopia, prevalence estimates vary significantly, reaching 31.5% in South Wollo (Adem et al., 2024) and 14.3% in Northwest regions (Alemu et al., 2020). Recent studies from Bangladesh according to Mahbub et al. (2024), the prevalence of CKD among T2DM patients in selected hospitals in Dhaka was found to be 34.5%, highlighting a critical public health issue. This aligns with global estimates but emphasizes regional variation due to socioeconomic, environmental, and healthcare access factors. These disparities reflect underlying differences in healthcare access, screening practices, and comorbid conditions, underscoring the need for targeted interventions and enhanced surveillance globally.

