Baseline evaluation: Patients with chronic kidney disease and type 2 diabetes will be screened consecutively and prospectively by the above inclusion and exclusion criteria to select eligible patients. Eligible patients and their legal relatives will be fully explained the study protocol, their role in the study, and the risk of the study. They will be enrolled in the study after getting written informed consent. Demographic and clinical information will be collected as per the case record form by interviewing the patients, reviewing the medical records, and performing physical examinations. After taking proper history and physical examinations, blood and urine samples will be collected for biochemical analysis. Blood tests will include measurement of Serum Creatinine, Estimated Glomerular Filtration Rate (eGFR), Serum Potassium, Fasting Blood Sugar (FBS), 2-Hour Postprandial Blood Sugar (2HPPBS) and HbA1C. Urine samples will be analyzed for Urine Albumin-Creatinine Ratio (first morning urine) and routine examination (R/E), including albumin, RBC and WBC. If a patient reports symptoms or any biochemical findings suggestive of a Urinary Tract Infection (UTI), a urine culture and sensitivity (C/S) test will be performed. Baseline clinical and laboratory parameters will be recorded in the case record form.

Randomization: Once a participant is enrolled in the study and consents to participate, they will be assigned to a treatment group according to the randomization sequence. Patients will be randomly assigned to either experimental groups or control group with a 1:1 ratio (block size of four). Randomization will be carried out using online software (Research Randomizer Version 4.0 at <https://www.randomizer.org>).

Blinding: The study will be open-label, with both participant and the researcher aware of their treatment allocation.

Treatments: The treatment phase lasted for eight weeks. The experimental group will receive oral dapagliflozin 10 mg plus Finerenone 10 mg daily. While the control group will receive oral dapagliflozin 10 mg daily. All the patients will be advised to follow standard dietary advice (including low salt <5gm/daily, diabetic diet), regular exercise, regular home capillary glucose monitoring & maintain all the standard pharmacological therapies throughout the study, including oral antidiabetic drug/insulin and any other antihypertensive medications (if required).

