In every visit, for blood test, blood will be collected from accessible vein with proper aseptic precaution and patient remained at least 8 hours overnight fasting before blood collection and blood was collected into red topped vacutainer. After collection of 10 mL blood, it will be allowed to clot by leaving it undisturbed at room temperature for 10-15 minutes and will removed the clot by centrifuging at 3000rpm for 10 minutes for serum. Serum creatinine concentration will be measured by buffer kinetic jaffe reaction using a SIEMENS dimension EXL200 analyzer while eGFR will be measured by CKD-EPI formula. The urinary albumin concentration was determined using a nephelometry method by BN pro-spec analyzer while urinary creatinine concentration was measured by endpoint spectrophotometric method with an alkaline picrate solution using a SIEMENS dimension EXL200 analyzer. UACR will be calculated by dividing the concentration of urinary albumin by the concentration of urinary creatinine. All the investigations will be performed in an ISO certified laboratory.

5.14. Data analysis:

Data will be recorded in the form of an Excel worksheet. After completion of data collection, data will be analyzed using the Statistical Package for Social Sciences (SPSS) version 27.0 (IBM Corp., Armonk, NY, USA). The continuous variables will be presented by measures of central tendency and measures of dispersion. For the normally distributed data, mean \pm standard deviation will be used, and for non-parametric data, median and Interquartile range (IQR) will be presented. On the other hand, we would present the categorical variables as frequency distribution. Between groups, comparisons of independent variables will be performed by independent t-test and Mann-Whitney U-test for normally and not-normally distributed variables respectively. Within patients, comparison will be performed by paired t-test or Wilcoxon Signed Rank Test, as appropriate. The Chi-square test will investigate the differences in categorical variables between two groups. Repeated measures ANOVA will be performed to compare mean values across multiple time points within the same group. Where appropriate, post-hoc analysis with Bonferroni correction will be conducted to identify specific time points with significant difference. A p-value <0.05 will be considered statistically significant.

[figure not shown]

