Appendix

Case record form

Protocol Title: Effect of dapagliflozin compared to dapagliflozin-finenone combination on albuminuria in patients with chronic kidney disease and type 2 diabetes: A randomized controlled trial.

Patient's identification			
1	Patient ID No.		
2	Name of the patient		
3	Contact no:		
4	Address:		
5	Study group: Group 1: Experimental group Group 2: Control group		
Demographic characteristics			
1	Age:years	
2	Sex:	0=Female 1=Male	
3	Place of residence	1=Urban, 0= Rural	
3	Monthly incomeBDT	
Clinical Characteristics			
1	Duration of Diabetes Mellitus years	
2	Duration of Hypertension years	
3	Current medication for DM	1=Insulin 2=Oral Hypoglycemic Agents 3=Both Insulin and Oral Hypoglycemic Agents	
4	Current medication for HTN	1=ACEi, 2=ARB, 3=MRA, 4=Beta blocker, 5=CCB, 6=Diuretics, 7=Others	
Clinical Parameters		Baseline	4 Weeks
1	Height (cm)		
2	Weight (kg)		
3	BMI (kg/m ²)		
4	Systolic BP (mmHg)		
5	Diastolic BP (mmHg)		
Biochemical Parameters		Baseline	4 Weeks
1	Serum Creatinine (mg/dL)		
2	eGFR (mL/min/1.73m ²)		
3	Serum Potassium (mmol/L)		
4	Fasting Blood Sugar (mg/dL)		
5	2-hour Postprandial Blood Sugar (mg/dL)		
6	Urine Albumin-Creatinine Ratio (UACR) (mg/g)		

7	Urine R/E – Albumin:			
8	Urine R/E – RBC:			
9	Urine R/E – WBC:			
	Biochemical Parameters	Baseline	4 Weeks	8 Weeks
10	HbA1C (%)		-	-
11	Urine Culture & Sensitivity (if UTI suspected):			
12	Vaginal discharge/penile swab for C/S (if genital mycotic infection suspected)	-		
13	Urine for ketone bodies (if DKA suspected)			
14	Serum bicarbonate (if DKA suspected)			

Adverse Effect			4 Weeks	8 Weeks
1	Hyperkalemia	1=Yes 2=No		
2	Hypotension	1=Yes 2=No		
3	UTI	1=Yes 2=No		
4	Genital Mycotic Infection	1=Yes 2=No		
5	Hypoglycemia	1=Yes 2=No		
6	Dizziness	1=Yes 2=No		
7	Constipation	1=Yes 2=No		
8	Acute Kidney Injury (AKI)	1=Yes 2=No		
9	Diabetic Ketoacidosis (DKA)	1=Yes 2=No		
10	Fournier's gangrene	1=Yes 2=No		
11	Expired	1=Yes 2=No		
12	Others	1=Yes 2=No		
Outcome		Completed per protocol=1, Withdrawn=2, Lost to follow up =3		

Signature of the researcher:

Signature of the Guide/Co-guide

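### The MRA exclusion is set in hours that, for finerenone and spironolactone, are shorter than a once-daily dosing interval, so as written it can admit ongoing MRA users to a trial whose control arm is meant to be dapagliflozin alone

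*Protocol*

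**What the plan says.** Section 5.8 (Exclusion criteria) does not bar MRA users outright. It excludes treatment with "MRAs (finerenone:10-20 hours, spironolactone:7 hours , eplerenone:15-30 hours) within their wash out periods". Finerenone and eplerenone are given as ranges, with no statement of which end applies. The next bullet is worded differently: it excludes patients who are on non-dihydropyridine calcium channel blockers or GLP-1 agonists, with no time limit.

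Four other places bear on the point:

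- The Part C summary gives the experimental regimen as "dapagliflozin 10 mg plus finerenone 10 mg once daily for eight weeks", so finerenone's dosing interval in this trial is 24 hours.
- Section 5.5 defines the control arm as dapagliflozin 10 mg without any second study drug.
- Section 5.13 (Treatments) tells all patients to "maintain all the standard pharmacological therapies throughout the study, including oral antidiabetic drug/insulin and any other antihypertensive medications (if required"). It makes no exception for MRAs.
- The variable list in section 5.10 includes MRAs among current antihypertensives. The case record form does the same, with the codes "1=ACEi, 2=ARB, 3=MRA, 4=Beta blocker, 5=CCB, 6=Diuretics, 7=Others". The form asks for this once, without visit columns.

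No section says that an MRA must be stopped before baseline, or that a non-study MRA is not allowed during the eight weeks.

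**The concern.** The trial estimates what finerenone adds to dapagliflozin. That requires control patients to be free of mineralocorticoid receptor blockade and experimental patients to have finerenone as their only source of it. An exclusion window shorter than the gap between two doses does not secure this, because a patient in the middle of uninterrupted treatment can fall outside it.

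If such patients enter and continue, a control patient receives the mechanism under test and an experimental patient may take two MRAs. The UACR contrast (specific objective 1) then shrinks towards the null. The potassium comparison (objective 2) and the safety comparison (objective 5) no longer describe finerenone plus dapagliflozin against dapagliflozin alone. Analysis could adjust for or describe background MRA use, but only if it is recorded through follow-up, and adjustment would not restore an MRA-free control arm.

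**Working it through.** **Step 1: windows against a 24-hour interval.** The windows come from section 5.8. The 24-hour interval is stated for finerenone (Part C summary); for spironolactone and eplerenone it is an assumption. Hours per day during which a patient who has missed no dose is outside the window = max(0, 24 − window).

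| Drug | Window (h) | Hours outside the window per 24 h |
|---|---|---|
| Finerenone, lower bound | 10 | 14 |
| Finerenone, upper bound | 20 | 4 |
| Spironolactone | 7 | 17 |
| Eplerenone, lower bound | 15 | 9 |
| Eplerenone, upper bound | 30 | 0 |
| Empagliflozin | 62 | 0 |
| Dapagliflozin | 65 | 0 |

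If dosing were every 12 hours, the figures would be 5 hours for spironolactone, 0 to 2 for finerenone and 0 for eplerenone. The gap therefore exists for finerenone and spironolactone at every stated once-daily value, for eplerenone only in the lower part of its range, and not for the SGLT2 inhibitors.

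**Step 2: does another section close the gap?** Section 5.13 points towards continuing background drugs. Section 5.10 and the case record form have a category for MRAs. Section 5.5 points the other way, since its control arm is dapagliflozin alone. Nothing decides between them.

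**Step 3: the plan's own sample size.** Section 5.9 uses p = 36%, q = 8%, z = 1.96 and z = 1.28:

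n = [36 × 64 + 8 × 92] / 28² × (3.24)² = 3040 / 784 × 10.4976 = 40.7

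The plan states about 40 per arm, and 40 × 1.10 = 44.

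**Step 4: illustration of dilution.** Let f be the share of patients in both arms who stay on an MRA, and r the fraction of finerenone's effect that remains in them. The average effect is multiplied by 1 − f(1 − r). Neither f nor r is in the document.

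Reading 36% and 8% as reductions, the ratio of UACR between arms is 0.64 / 0.92 = 0.70, and ln 0.696 = −0.363. A log-scale SD of 0.494 gives 90% power at 40 per arm. That SD is back-solved, not a document value. Power is from the noncentral t distribution (two-sided 0.05, 78 degrees of freedom).

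| f | r | Log effect | Ratio | Power |
|---|---|---|---|---|
| 0 | – | −0.363 | 0.70 | 90% |
| 10% | 0 | −0.327 | 0.72 | 83% |
| 20% | 0 | −0.290 | 0.75 | 74% |
| 10% | 0.5 | −0.345 | 0.71 | 87% |
| 20% | 0.5 | −0.327 | 0.72 | 83% |

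**Cross-check on the plan's own proportion scale.** The 28-point difference becomes 28 × (1 − f) with r = 0. At 40 per arm the section 5.9 formula gives 89.5% power at f = 0, 83.5% at f = 10% (25.2 points) and 75.6% at f = 20% (22.4 points). The two scales agree closely.

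**The case against.** The strongest reply is that a washout ordinarily starts when a drug is stopped, so the gap between two doses of a continuing drug is not one. On that reading MRA users must stop, and section 5.5 supports it. This is plausible as intent. But no section states it, section 5.13 has background therapy continue, and the neighbouring bullet shows that a plain bar on current users was available and was not used for MRAs. Even if stopping is meant, the ranges leave the cut-off for finerenone and eplerenone undefined, and nothing says the drug stays stopped.

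The reply is right to limit the point in several ways. A reader might infer the following, which the documents do not support:

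- **That the case record form expects MRA users.** It is a generic list of drug classes. It also carries an undivided calcium channel blocker code although one subclass is excluded, so the codes were not tailored to eligibility.
- **That the 8-hour overnight fast already exceeds the spironolactone window.** Fasting is set for blood collection and says nothing about when tablets were last taken.
- **That recent SGLT2 inhibitor use dilutes the contrast too.** Those windows exceed 24 hours and both arms receive dapagliflozin. A lower baseline in both arms leaves the added effect of finerenone intact on a ratio scale. The same holds for an MRA that was truly stopped; only continued use dilutes.
- **That the result would be biased towards finerenone.** Randomisation balances background use in expectation.

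It is also fair that zero finerenone effect in MRA users is the extreme case, and that the rationale in section 2 mentions limited access to advanced renal therapies, which hints at low background finerenone use. It says nothing about spironolactone.

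**Conclusion.** The point holds as a defect of the written rule. Section 5.8, applied literally, can admit patients on uninterrupted finerenone or spironolactone, and eplerenone at its lower bound. Nothing elsewhere stops the drug from continuing in either arm, contrary to section 5.5. For spironolactone and eplerenone this rests on assumed once-daily use.

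The consequence is loss of power and a potassium and safety comparison that is harder to interpret, not systematic bias. Its size cannot be fixed, because the share of such patients is unknown. For shares of 10% to 20%, a design with 90% power would have about 83% to 74% if finerenone adds nothing in them, and about 87% to 83% if half its effect remains. These figures assume equal use in both arms, an unchanged SD and the back-solved SD of 0.494. The change should be made before enrolment, since an MRA-free comparison cannot be recovered afterwards.

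**What to change.** Reconcile sections 5.5, 5.8, 5.10 and 5.13 and the case record form so that they say the same thing on three matters:

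1. Whether non-study MRA use is permitted at baseline and during the eight weeks. The sentence on keeping standard therapies in section 5.13 should match the answer.
2. One unambiguous cut-off per drug in section 5.8 in place of the ranges, counted from the time the drug is stopped.
3. How non-study MRA use is recorded. The case record form should capture it at each visit, in line with the rule, so that any departure is visible in the analysis.

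The rule itself and the length of any interval are for the clinical team to set.

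The cost is the wording of one criterion, a sentence in section 5.13, and a change to one item of the form and its matching entry in section 5.10. The downside is that, depending on the rule chosen, some screened patients may become ineligible or be delayed.

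### Minor: the section 5.9 formula gives 40.70, not 40, and adding 10% does not offset 10% loss, so 44 per group gives about 89% by that formula rather than 90%

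*Protocol*

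**What the plan says.** Protocol section 5.9 introduces its calculation as "Sample size calculation for hypothesis testing of difference between two proportions". The constants are "Z_{α} = 1.96 at 95% Confidence Interval" and "Z_{β} = 1.28 at 90% power". The two inputs are 36% for the experimental group and 8% for the control group. The section prints the formula with these values in place and gives the result as approximately 40 per group.

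The attrition step follows: "Considering 10% lost to follow-up final sample will be" 40 plus 10% of 40, which is 44. The section concludes: "That means 44 patients in each group will be needed to test the hypothesis". The Summary in Part C carries the doubled figure, describing a trial "including 88 patients with chronic kidney disease and type 2 diabetes".

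**The concern.** The sample-size line shows every input, so any reader can recompute it, and it does not give what it states. There are two separate slips.

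- **Rounding.** The formula's result lies above 40.5 but is written as 40. Ordinary rounding gives 41. So does the sample-size convention of rounding up, which ensures that the target power is reached.
- **Attrition.** Adding 10% of the evaluable number is not the inverse of losing 10% of the randomised number. The inverse is division by 0.90.

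Both slips lower the number, so they add up. At stake is whether 44 per group, with the 10% loss that the section itself allows for, delivers the 90% power that it claims by its own formula.

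**Working it through.** **Inputs, all from Protocol section 5.9:** p = 36, q = 8 (in percent), z for significance 1.96, z for power 1.28, loss to follow-up 10%.

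**1. The protocol's figure before loss.**

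n = [p(100 − p) + q(100 − q)] / (p − q)² × (1.96 + 1.28)²

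- Numerator: 36 × 64 + 8 × 92 = 2304 + 736 = 3040
- Denominator: 28² = 784
- Ratio: 3040 / 784 = 3.8776
- (3.24)² = 10.4976
- n = 3.8776 × 10.4976 = 40.70

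The protocol writes 40; 40.70 rounds to 41. Unrounded z values give 40.74, which also rounds to 41.

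**2. The protocol's attrition step.** 40 × 1.10 = 44, exactly as stated. Taking 10% off again gives 44 × 0.90 = 39.6, which is below even the protocol's own 40.

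**3. The step that keeps the evaluable number.** Randomised n = evaluable n / (1 − 0.10).

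- From 41: 41 / 0.90 = 45.6, so 46 per group and 92 in total. Check: 46 × 0.90 = 41.4.
- From the protocol's 40: 40 / 0.90 = 44.4, so 45 per group.

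**4. Power by the same formula.** Solving the formula for power gives Φ(√(n / 3.8776) − 1.96), where n is the evaluable number per group.

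| Evaluable per group | Meaning | Power by the 5.9 formula |
|---|---|---|
| 39.6 | 44 less 10% | 89.2% |
| 40 | the protocol's rounded figure; 44 less 4 patients (9.1%) | 89.5% |
| 41 | 40.70 rounded up; 44 less 3 patients (6.8%) | 90.2% |

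At 39.6 the steps are 39.6 / 3.8776 = 10.213, whose square root is 3.196, less 1.96 = 1.236, and Φ(1.236) = 0.892.

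**5. Shortfall.** 90 − 89.2 = 0.8 percentage points, or 46 − 44 = 2 patients per group (4 in total).

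**The case against.** The strongest reply is that the gap does not matter. The protocol marks its result as approximate, and 0.8 points is smaller than the effect of choosing another standard version of the formula. With a pooled variance, the same inputs give 44 evaluable per group, and 86.7% power at 39.6. No design decision turns on a difference of this size. This stands, and it is why the point is minor. It does not make the printed line right: 40.70 is not 40, and 44 does not leave 40 after 10% loss.

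A second reply is that the correction polishes a number with little meaning. Section 5.9 defines its input this way: "p = Percent change from baseline in UACR after treatment in the experimental group". UACR is listed as continuous in section 5.10, and its change is the primary outcome in the Summary. Percent changes in a continuous measure have been used as if they were proportions of patients, with no standard deviation. This also stands. Neither 44 nor 46 per group establishes power for the comparison of change in UACR, and correcting the rounding and the attrition step does not repair that. The corrected figures hold only on the formula's own terms and must be labelled so.

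Two stronger readings are tempting, and the protocol supports neither.

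- A reader might round 39.6 down to 39 evaluable per group and quote the lower power. But 5 lost of 44 is 11.4%, more than the 10% that the section assumes.
- A reader might infer that real attrition will be well above 10%, because section 5.11 F lists seven withdrawal criteria and the case record form codes withdrawal apart from loss to follow-up. The protocol gives no expected frequency for these withdrawals. Section 5.13 also asks withdrawn patients to return for a final visit where applicable and seeks to document outcomes in any circumstance. Withdrawal is therefore not the same as a missing outcome, and a higher attrition figure would have no source in the document.

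**Conclusion.** Wrong as written, but minor. On its own terms the section 5.9 formula requires 41 evaluable patients per group. Allowing for 10% loss then requires 46 randomised per group (92 in total), where the protocol has 40, 44 and 88. With 44 randomised and 10% lost, the same formula gives about 89.2% rather than 90%, a shortfall of under 1 percentage point.

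This rests on the protocol's own inputs, its unpooled two-proportion formula and its 10% loss, with nothing brought in from outside. It does not show that the trial is underpowered. A reader might take 89% as the true power for the primary outcome, but the formula does not address that comparison, so it supports neither 89% nor 90% there.

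**What to change.** Correct section 5.9 without enrolling more patients. It should state that:

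- the formula gives 40.70, so 41 evaluable per group;
- 10% loss would need 41 / 0.90, so 46 randomised per group (92 in total);
- the planned 44 per group (88 in total) gives about 89% by this formula after 10% loss;
- this figure is not a power for the comparison of change in UACR as a continuous outcome.

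If the formula is replaced by one suited to that outcome, these particular numbers fall away. The new calculation should still round up and divide by one minus the attrition rate.

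The cost is a few lines of text and a slightly less favourable stated figure. The Summary's total of 88 can stay.
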